3.3 EVALUATIONS WEEKS 1-10 {ALL EVALUATIONS ARE +/- 3 DAYS}

- Week 2-10:
 - Serum valproic acid levels may be performed weekly on all patients for at least the first 4 weeks of treatment.
 - Reports from all evaluations performed at outside institutions will be faxed to:

[name] or [name]
[contact]

This includes lab values, physical exams, patient diaries, etc.

- Week 2 (Day 10):
 - Physical exam including ECOG status
 - CBC with differential, platelets, BUN, creatinine, total protein, total bilirubin, ALT, AST, ALKP, amylase, ammonia, albumin and b-HCG (if applicable).
 - Toxicity assessment, pill count, and review of diary
- Week 4 – may be performed by their primary physicians
 - Physical exam including ECOG status
 - CBC with differential, platelets, BUN, creatinine, total protein, total bilirubin, ALT, AST, ALKP, amylase, ammonia, albumin and b-HCG (if applicable).
 - Toxicity assessment, pill count, and review of diary

- Week 6:
 - Physical exam including ECOG status
 - CBC with differential, platelets, BUN, creatinine, total protein, total bilirubin, ALT, AST, ALKP, amylase, ammonia, albumin and b-HCG (if applicable).
 - Toxicity assessment, pill count, and review of diary
- Week 8 - may be performed by their primary physicians
 - Physical exam including ECOG status
 - CBC with differential, platelets, BUN, creatinine, total protein, total bilirubin, ALT, AST, ALKP, amylase, ammonia, albumin and b-HCG (if applicable).
 - Toxicity assessment, pill count, and review of diary
- Week 10:
 - Physical exam including ECOG status
 - CBC with differential, platelets, BUN, creatinine, total protein, total bilirubin, ALT, AST, ALKP, amylase, ammonia, albumin and b-HCG (if applicable).
 - Serum valproic acid levels.
 - Toxicity assessment, pill count, and review of diary
 - Tg, TSH
 - Thyrogen Scan
 - Health Related Quality of Life HRQOL) form completion
 - Tumor tissue biopsy of any accessible lesions (Section 3.7)
 - 24 hour urinary iodine level

3.4 THYROGEN RAI SCAN

All patients will undergo a Thyrogen® (thyrotropin alfa for injection) RAI scan at entry to the study and after completion of 10 weeks of valproic acid treatment. Depending on the results of the scan, patients will continue valproic acid and prepare for an ablation, or will continue with valproic acid.

Procedure:

- Low iodine diet for 2 weeks
- Thyrogen 0.9mg intramuscularly (in the buttocks) every 24 hours x 2 doses
- 123-I radioiodine 24 hours following the last dose of Thyrogen
- Serum Tg and TSH **immediately** prior to the scan
- Scan 48 hours after radioiodine administration (72 hours after thyrogen administration)

3.5 PHASE 2 WEEKS 11-16

3.5.1 Schedule 1 - Patients who exhibit an increased radioiodine uptake on Thyrogen scan post valproic acid therapy at week 10.

- Week 11:
 - Discontinue Levothyroxine
 - Begin Cytomel for 4 weeks (25 micrograms twice a day)
 - Continue valproic acid for a total of 16 weeks

Note: medication will be dispensed following review of Thyrogen scan
- Week 12 - may be performed by their primary physicians
 - Physical exam including ECOG status
 - CBC with differential, platelets, BUN, creatinine, total protein, total bilirubin, ALT, AST, ALKP, amylase, ammonia, albumin and b-HCG (if applicable).
 - Toxicity assessment, pill count, and review of diary
- Week 14: may be performed by their primary physicians
 - Physical exam including ECOG status
 - CBC with differential, platelets, BUN, creatinine, total protein, total bilirubin, ALT, AST, ALKP, amylase, ammonia, albumin and b-HCG (if applicable).
 - Toxicity assessment, pill count, and review of diary
 - Stop Taking Cytomel.
 - Begin low iodine diet.
- Week 16:
 - Measure TSH, Tg and 24 hour urinary iodine.
 - I-131 Ablative treatment {refer to Section 3.6}.
 - Physical exam including ECOG status
 - CBC with differential, platelets, BUN, creatinine, total protein, total bilirubin, ALT, AST, ALKP, amylase, ammonia, albumin and b-HCG (if applicable).
 - Toxicity assessment, pill count, and review of diary
- Week 17:
 - Post ablation RAI scan {5 days (+/- 2 days) following administration of 131-I}.
 - Ultrasound of the neck
 - MRI or CT of the neck and chest
 - FDG-PET scan
 - Resume Levothyroxine (pre study dose) .

- Stop valproic acid end of week 17
- Toxicity assessment, pill count, and review of diary
- Health Related Quality of Life HRQOL) form completion

3.5.2 Schedule 2 – patients who do not exhibit an increased radioiodine uptake on Thyrogen scan post valproic acid therapy at week 10

- Week 11:
 - Maintain valproic acid dose
- **Note:** medication will be dispensed following review of the Thyrogen scan.
- Week 12:
 - Physical exam including ECOG status
 - CBC with differential, platelets, BUN, creatinine, total protein, total bilirubin, ALT, AST, ALKP, amylase, ammonia, albumin and b-HCG (if applicable).
 - Serum valproic acid levels.
 - Toxicity assessment and review of diary
- Week 14: may be performed by local physician
 - Physical exam including ECOG status
 - CBC with differential, platelets, BUN, creatinine, total protein, total bilirubin, ALT, AST, ALKP, amylase, ammonia, albumin and b-HCG (if applicable).
 - Toxicity assessment and review of diary
- Week 16:
 - Physical exam including ECOG status
 - CBC with differential, platelets, BUN, creatinine, total protein, total bilirubin, ALT, AST, ALKP, amylase, ammonia, albumin and b-HCG (if applicable).
 - Tg, TSH
 - Toxicity assessment and review of diary
 - Ultrasound of the neck and mediastinum
 - MRI or CT of the neck and chest
 - FDG-PET scan
 - Health Related Quality of Life HRQOL) form completion
- Weeks 17-52
 - Patients who show a response by RECIST criteria or have a decreased thyroglobulin level from Day 1 of the treatment (registered as a partial response to the treatment) will continue on valproic acid at their current dose for a total of 52 weeks.

- Stop valproic acid if no response
- Sixteen weeks or 4 months is significant amount of time to measure response to treatment and therefore, if there is a response, a patient's thyroglobulin levels should have decreased by then, as well as, by RECIST criteria.
- Patients who show no response, patients will stop valproic acid treatment and continue with routine follow up.

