3 STUDY IMPLEMENTATION

3.1 STUDY DESIGN

Current conventional therapy for patients with thyroid cancers of follicular cell origin after thyroidectomy and ablative treatment with 131-I involves only thyroid hormone for TSH suppression. In this study, patients will receive TSH suppression therapy with valproic acid for 16 weeks.

The total study period will be 18 weeks, with a one year follow up. Patients who respond to treatment as evidenced by decreased Tg level, RAI uptake or decreased tumor size will continue treatment of valproic acid for 1 year.

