5.2 RESPONSE CRITERIA

RAI uptake and Tg level will be compared pre- and post-valproic acid treatment. The nuclear medicine radiologists using a planar technique will measure the RAI scan uptake. The post-valproic acid scan will then be compared side-to-side with the pre-valproic acid scan, using the planar technique, and will then be scored as "increased" or "unchanged" compared to zero/minimal (<1%) uptake seen on the pre-valproic acid scan. We will define 4 categories of response:

1. Complete response: increased RAI uptake on post-valproic acid therapy at week 10, AND a decrease in Tg level to less than 2 ng/ml (or a decrease in Tg-Ab level to less than 2.0 IU/ml) at 10 weeks AND disappearance of all lesions at 16 weeks.
2. Partial response: increased RAI uptake on post-valproic acid scan at week 10, OR a decreased Tg level (or a decrease in Tg-Ab level by more than 20%) at 10 weeks AND 30% decrease in target lesion at 16 weeks.
3. Stable disease: no change in RAI uptake AND Tg levels (or Tg-Ab level) AND no significant change of lesions 16 weeks.
4. Progressive disease: tumor mass increases OR Tg levels (or Tg-Ab levels) increases over 10 weeks OR at least 20% increase in target lesion at 16 weeks.

Target lesions will be evaluated according to the RECIST response criteria outlined below.

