6.2 SAMPLE SIZE AND POWER ANALYSIS

This is a phase II study aimed at measuring the impact of valproic acid on iodine uptake and on tumor response. Response will be defined as complete or partial response as outlined in section 5.2. The study uses a two-stage Simon optimal design with an interim analysis planned when 13 patients are evaluable for response. If no complete/partial responses are seen at that time the study will close to accrual. The study will proceed to stage II if at least one response is seen among the first 13 patients. At the end of study, if the cumulative number of responses among the 20 evaluable patients is 3 or more, valproic acid will be considered efficacious, while this will not be the case if 1-2 responses are noted. Under the null hypothesis of a true response rate that does not exceed 5% ($p_0=0.05$), the two-stage design will control type I error (α) to be no more than 7.4%, and when the true response rate is at least 25% ($p_1=0.25$), the study has at least 90% power ($\beta=0.10$). The probability of triggering early stopping is at least 51% if the true response rate is 5% or less, and less than 2.5% if the true response rate is 25% or more. If the accrual is stopped at the first stage due to futility, the upper bound of a 95% confidence interval for the response rate will be less than 25%. We will plan to enroll up to 25 patients with the expectation that 20 patients (80%) will be evaluable for response.

The stopping rule for Grade 3 toxicity is set at 15% as the acceptable toxicity rate because the study is designed to detect a treatment efficacy rate of 15% or higher. Therefore, if the acceptable toxicity rate is higher than the expected efficacy rate the study will be stopped.

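### Section 3.5.2 registers a partial response on any thyroglobulin fall in Schedule 2 patients, which section 5.2, the basis of the Simon count, does not accept

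*Protocol*

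**What the plan says.** Schedule 2 in Protocol section 3.5.2 is for "patients who do not exhibit an increased radioiodine uptake on Thyrogen scan post valproic acid therapy at week 10". Its entry for weeks 17 to 52 concerns "Patients who show a response by RECIST criteria or have a decreased thyroglobulin level from Day 1 of the treatment". These patients continue valproic acid, and a parenthesis attached to the Tg phrase adds the registration: "have a decreased thyroglobulin level from Day 1 of the treatment (registered as a partial response to the treatment". A later bullet in the same entry, on sixteen weeks being long enough to judge response, says "a patient's thyroglobulin levels should have decreased by then, as well as, by RECIST criteria".

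The four-category definition in section 5.2 begins "Partial response: increased RAI uptake on post-valproic acid scan at week 10, OR a decreased Tg level". The second part of that line is "a decreased Tg level (or a decrease in Tg-Ab level by more than 20%) at 10 weeks AND 30% decrease in target lesion", with the lesion assessed at 16 weeks. Section 5.2.1.3, a subsection of 5.2, has its own RECIST table of overall response, based on lesions.

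Section 6.2 states: "Response will be defined as complete or partial response as outlined in section 5.2". Accrual closes if there is no response among the first 13 evaluable patients. Three or more responses among 20 count as efficacy.

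**The concern.** Section 3.5.2 uses the endpoint's own category name, partial response, for a state that the endpoint definition does not recognise. A rule for continuing treatment may properly be looser than the endpoint. An instruction to register the looser state under the endpoint's name is different, because it puts two kinds of partial response into the same record.

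Both decisions in 6.2 turn on very few patients. If Tg-only registrations were carried into the count, the 5% null rate, the 7.4% type I error and the 51% chance of early stopping would no longer describe what is being counted. Because any decrease from Day 1 qualifies, ordinary variation in a repeated Tg measurement could produce such registrations.

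**Working it through.** **1. The plan's own figures.** Inputs from section 6.2: 13 patients in stage 1, stop at 0 responses, 20 in total, success at 3 or more, null rate 5%, target rate 25%. For a response rate p:

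- P(early stop) = (1 − p)^13
- P(success) = P(Bin(20, p) ≥ 3) − (1 − p)^13 × P(Bin(7, p) ≥ 3)

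The subtracted term removes trials that stop at 0 of 13 but would have reached 3 in the last 7 patients.

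- p = 0.05: early stop 0.95^13 = 0.513; success 0.0755 − 0.513 × 0.0038 = 0.0736.
- p = 0.25: early stop 0.75^13 = 0.024; success 0.9087 − 0.0238 × 0.2436 = 0.903.

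These agree with the stated 7.4%, 51%, under 2.5% and 90%.

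**2. The two definitions for a Schedule 2 patient.** Let A = increased uptake at week 10, B = Tg or Tg-Ab fall at week 10, C = 30% lesion decrease at week 16, T = Tg fall from Day 1 as seen at week 16. The OR/AND in 5.2 can be grouped as (A or B) and C, or as A or (B and C). In Schedule 2, A is false, so both reduce to B and C. The 5.2 complete response also requires increased uptake, so it cannot occur here.

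| B | T | C | 5.2 partial response (either grouping) | 3.5.2 registration on Tg |
|---|---|---|---|---|
| no | no | no | no | no |
| no | no | yes | no | no |
| no | yes | no | no | **yes** |
| no | yes | yes | no | **yes** |
| yes | no | no | no | no |
| yes | no | yes | **yes** | no |
| yes | yes | no | no | **yes** |
| yes | yes | yes | **yes** | **yes** |

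A Tg fall without shrinkage (third and seventh rows) is registered under 3.5.2 and is never a partial response under the 5.2 line. It is not one under 5.2.1.3 either, where an overall partial response needs a complete or partial response of the target lesions.

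**3. Consequence without any assumed rate.** With no 5.2 response among 13, one Tg-only registration, if counted, turns closure into continuation. With no 5.2 response among 20, three of them turn a negative result into a positive one, provided at least one falls among the first 13.

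**4. Illustration.** The documents give no rate of Tg fall without shrinkage. Assume a true 5.2 rate of 5%, and that a share x of all 5.2 non-responders is registered on Tg alone and counted along with the 5.2 responders. The counted rate is then p = 0.05 + 0.95x. From the formulas in step 1:

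| x | p | P(declared efficacious) | P(early stop) |
|---|---|---|---|
| 0 | 0.0500 | 7.4% | 51% |
| 5% | 0.0975 | 30% | 26% |
| 10% | 0.1450 | 56% | 13% |
| 20% | 0.2400 | 89% | 3% |

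Only Schedule 2 patients can be registered this way. Hence x = s × q, where s is the share of non-responders who are in Schedule 2 and q the chance of a Tg-only registration among them. Under A or (B and C), every Schedule 1 patient is a responder, so s = 1. Under (A or B) and C, Schedule 1 patients without shrinkage are also non-responders, so s can be lower. If s were one half, q = 10% would give x = 5% and 30%, and q = 20% would give x = 10% and 56%.

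**The case against.** The strongest reply is that 6.2 already names 5.2 as the definition that governs the count. Section 3.5.2 belongs to the treatment schedule, decides who continues, and mentions neither the interim nor the final count. This stands: the stated operating characteristics are correct as written, and inflation arises only if 3.5.2 registrations are counted. It does not remove the conflict, because staff are told to register a partial response for patients who have none under 5.2.

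Three stronger readings are tempting and are not supported.

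- A reader might infer that 3.5.2 also registers a RECIST response alone, and that 5.2 forbids this throughout. But the parenthesis directly follows the Tg phrase, and the 5.2.1.3 table, inside 5.2, gives an overall partial response on lesions with no Tg condition.
- A reader might infer that the type I error in 6.2 is wrong. It recomputes to 7.36%.
- A reader might infer that the two responder groups do differ in a known number of patients. The documents show only that they can differ.

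Three smaller points also stand. Week 16 is inferred for the 3.5.2 assessment from the Tg draw scheduled then and the sixteen-week bullet; the clause itself fixes only the Day 1 baseline. That bullet expects Tg and RECIST to move together, which leans towards the joint criterion and leaves 3.5.2 inconsistent with itself. Section 3.9.1 takes patients with progressive disease off therapy, so some never reach the decision.

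Section 3.1 has similar wording, "Patients who respond to treatment as evidenced by decreased Tg level, RAI uptake or decreased tumor size will continue treatment", but it concerns continuation and registers nothing.

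**Conclusion.** The concern holds for the Tg-only limb. In Schedule 2 patients, 3.5.2 registers a partial response on any Tg decrease from Day 1, while neither the 5.2 line (under either grouping) nor the 5.2.1.3 table does so. This is an internal contradiction and needs no assumption.

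Its effect on the trial is conditional. If only 5.2 responses are counted, the 7.4% type I error and 90% power stand. If Tg-only registrations enter the count, one or three patients are enough to reverse a decision. The figures of 30%, 56% and 89% illustrate that sensitivity under an assumed share x of all 5.2 non-responders; they do not predict what will happen.

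A related gap remains. Section 5.2 holds both the four-category composite, with its unresolved OR/AND, and a lesion-only RECIST overall response, and 6.2 does not say which it means. Repeating that 5.2 governs would therefore not settle the count.

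**What to change.** 1. In 3.5.2, delete the parenthetical remark about registration as a partial response. Record the signal for continuing treatment in a separate field under a different name.
2. Reconcile 3.5.2, 5.2 and 5.2.1.3.
3. In 6.2, state the single definition that alone drives the 0-of-13 and 3-of-20 decisions: either the 5.2 composite, with its OR/AND grouping made explicit, or the RECIST overall response. Confirm that the 5% and 25% rates were meant for the definition chosen.

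Who continues treatment is left to the investigators.

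The cost is wording in four places and one database field. No patients or procedures are added: week-10 Tg and week-16 imaging are already scheduled, so any patient already registered on Tg alone can be classified from existing data. The wording should be settled before the interim count.

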3.9 CRITERIA FOR REMOVAL FROM PROTOCOL THERAPY AND OFF STUDY CRITERIA

3.9.1 Criteria for removal from protocol therapy

- Patient request
- PI discretion, if the PI feels it is not in the best interest of the patient to remain on treatment
- Liver Dysfunction (enzyme levels above 1.5 times ULN)
- Platelet < 50,000
- Ammonia levels > 65 mol/l
- Progressive disease
- Pregnancy
- Pancreatitis (amylase level above 1.5 ULN)
- Alcohol consumption
- Other unacceptable toxicities as determined by the PI

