5.2.1 Response Criteria RECIST 1.1

5.2.1.1 Evaluation of target lesions*

- Complete Response (CR): Disappearance of all target lesions. Any pathological lymph nodes (whether target or non-target) must have reduction in short axis to <10 mm.
- Partial Response (PR): At least a 30% decrease in the sum of diameters of target lesions taking as reference the baseline sum diameters.
- Progression (PD): At least a 20% increase in the sum of diameters of target lesions taking as reference the smallest sum on study (this includes the baseline sum if that is the smallest on study) or the appearance of one or more new lesions.

- Stable Disease (SD): Neither sufficient shrinkage to qualify for PR nor sufficient increase to qualify for PD taking as references the smallest sum diameters while on study.

* *All measurable lesions up to a maximum of 5 lesions (and a maximum of 2 lesions per organ) representative of all involved organs should be identified as **target lesions** and recorded and measured at baseline. Target lesions should be selected on the basis of their size (lesions with the longest diameter), be representative of all organs involved, and be suitable for accurate repetitive measurements (either by imaging techniques or clinically). A sum of the diameters (longest for non-nodal lesions, short axis for nodal lesions) for all target lesions will be calculated and reported as the baseline sum diameters. The baseline sum diameters will be used as reference to further characterize the objective tumor response of the measurable dimension of the disease.*

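### Section 3.5.2 registers any thyroglobulin fall from Day 1 as a partial response, but for the same patients section 5.2 also requires a 30% target-lesion decrease

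*Protocol*

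**What the plan says.** Section 3.5.2 covers Schedule 2, the patients without increased RAI uptake on the week 10 Thyrogen scan. For weeks 17 to 52 it continues drug in those with a RECIST response and in those who "have a decreased thyroglobulin level from Day 1 of the treatment (registered as a partial response to the treatment) will continue on valproic acid". The Tg route has no threshold and no lesion condition.

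Section 5.2 defines partial response by an RAI uptake increase on the week 10 scan, joined by OR to the following: "decreased Tg level (or a decrease in Tg-Ab level by more than 20%) at 10 weeks AND 30% decrease in target lesion at 16 weeks". Stable disease there is "no change in RAI uptake AND Tg levels (or Tg-Ab level) AND no significant change of lesions 16 weeks". Progressive disease is any one of: an increase in tumor mass, a rise in Tg or Tg-Ab over 10 weeks, or "at least 20% increase in target lesion at 16 weeks". The RECIST text in 5.2.1.1 sets progression at "At least a 20% increase in the sum of diameters of target lesions", or new lesions.

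Section 6.2 fixes the endpoint: "Response will be defined as complete or partial response as outlined in section 5.2".

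On stopping drug, section 3.9.1 lists "Progressive disease" among the reasons for removal from protocol therapy. Section 3.1 says that patients who respond "as evidenced by decreased Tg level, RAI uptake or decreased tumor size will continue treatment of valproic acid for 1 year".

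**The concern.** The protocol gives two different tests for the same label in the same patients. Section 3.5.2 is an operational instruction that clinical and data staff will follow at week 16, and it tells them to register a partial response on Tg alone. Section 5.2, on which the primary endpoint rests, does not allow that.

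The gap in 5.2 makes confusion more likely. A patient whose Tg has fallen while the lesions are unchanged fits none of its four categories read literally, so the only composite label the protocol offers is the one in 3.5.2.

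The decision limits are small: at least 1 response in 13 to continue accrual and at least 3 in 20 to call the drug efficacious. A very few misregistered patients could change either decision.

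**Working it through.** **1. The two definitions for a Schedule 2 patient**

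Let A = increased RAI uptake at week 10, B = Tg decrease (or Tg-Ab decrease of more than 20%) at week 10, and C = 30% target-lesion decrease at week 16. Section 5.2 can be grouped in two ways:

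- A OR (B AND C)
- (A OR B) AND C

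Schedule 2 is defined by A being false. Both groupings then reduce to B AND C. The ambiguity in 5.2 therefore does not matter for these patients: a marker fall and 30% shrinkage are both needed.

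Section 3.5.2 asks only for D = Tg below its Day 1 level. D does not imply C. Nor does it imply B, because 5.2 looks at week 10 while the 3.5.2 decision follows the week 16 assessment.

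**2. Placing patients in the two sections**

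| Schedule 2 patient | Section 5.2 | Section 3.5.2 |
|---|---|---|
| Tg down at weeks 10 and 16, lesions down 30% | Partial response | Partial response |
| Tg down at weeks 10 and 16, lesions unchanged | No category: not complete (A false), not partial (C false), not stable (Tg changed), not progressive | Partial response |
| Tg up over 10 weeks, below Day 1 at week 16, lesions unchanged | Progressive disease | Partial response |
| Tg down at weeks 10 and 16, target lesions up 20% | Progressive disease | Partial response |

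The sections agree only in the first row. For the second row, the lesion criteria alone (5.2.1.1) give stable disease.

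**3. The decision rule in section 6.2**

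Inputs from 6.2: 13 patients in stage 1, stop if there are 0 responses; 20 in total, success if there are 3 or more; null rate 5%, target rate 25%.

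P(efficacious) = sum over x = 1 to 13 of P(Bin(13, p) = x) × P(Bin(7, p) ≥ 3 − x)

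P(early stop) = (1 − p)^13

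| Quantity | Computed | Stated in 6.2 |
|---|---|---|
| P(efficacious), p = 0.05 | 0.0736 | no more than 7.4% |
| P(efficacious), p = 0.25 | 0.9030 | at least 90% |
| P(early stop), p = 0.05 | 0.513 | at least 51% |
| P(early stop), p = 0.25 | 0.0238 | less than 2.5% |

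The design figures are correct. They hold for a response as defined in 5.2.

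**4. Effect of one patient counted under the 3.5.2 label**

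- Interim: 0/13 becomes 1/13 = 7.7%, and stopping becomes continuing.
- Final: 2/20 becomes 3/20 = 15%, and not efficacious becomes efficacious.

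The documents do not say how often Tg falls without lesion shrinkage, so the probability of such a reversal cannot be calculated from them.

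**The case against.** The strongest reply is that the primary endpoint is already protected. Section 6.2 refers to 5.2 and not to 3.5.2, so counting a Tg-only patient would breach 6.2, and any misclassified patient near a boundary would have the same effect. This stands. It limits the consequence to the case where the 3.5.2 label is carried into the count. A reader might infer that the true type I error exceeds 7.4%. The documents do not support that: they tie the count to 5.2 and give no rate of Tg-only falls, so any inflated figure would rest on an invented rate.

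A reader might also infer that drug is continued to week 52 regardless of tumor growth, up to 52 − 16 = 36 weeks beyond the week 16 scan. That is true only of 3.5.2 read in isolation. Section 3.9.1 removes patients with progressive disease and also allows removal at the principal investigator's discretion. A removal list ordinarily applies on top of every schedule: 3.5.2 does not repeat pregnancy or a low platelet count either, and nobody would take it to continue drug through those. Continuation is therefore a matter of clarity, not a demonstrated conflict.

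Finally, the same block of 3.5.2 remarks that by 16 weeks a responder should show both a Tg decrease and a RECIST response. This suggests that the authors expected the two to move together. It bears on intent, but it does not change the *or* in the operative sentence or the label attached to it.

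**Conclusion.** The label conflict is established from the text and does not depend on how 5.2 is parsed. Section 3.5.2 registers as a partial response a Schedule 2 patient who is not one under 5.2, and a Tg fall with stable lesions has no category in 5.2. The second part rests on reading the stable-disease definition literally, as requiring unchanged Tg.

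The effect on the primary result is conditional. It is nil if 6.2 is followed. If the 3.5.2 label is used, one patient is enough to reverse a decision at either boundary.

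The missing progression limit in 3.5.2 and 3.1 is secondary and calls for clarification. The point should be fixed because the instruction is wrong as written and cheap to correct.

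**What to change.** 1. In 3.5.2, delete the parenthesis that registers a Tg decrease as a partial response, and state that response for section 6.2 is classified by section 5.2 only.
2. In 5.2, state that a Schedule 2 patient with a Tg or Tg-Ab decrease, without the 30% lesion decrease and without progressive disease, is classified as stable disease and is not a response.
3. In 3.5.2 and in the 1-year sentence of 3.1, add: *provided there is no progressive disease as defined in sections 5.2 and 5.2.1; section 3.9.1 applies throughout*. The proviso should refer to the whole definition and not only to 20% growth, because 5.2 also counts a tumor mass increase and a Tg or Tg-Ab rise over 10 weeks as progression.

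The cost is amendment wording in three places, with no added patients, visits or tests. Whether to continue drug on a Tg fall without progression remains the investigators' choice.
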